6.3 Surgery and Post-treatment Tumor Tissue Collection

6.3.1 Days 11-22 (window of +7 days up to day 29, inclusive of day of surgery)

- Oncologic head and neck cancer surgery
 - After 10-21 days of neoadjuvant treatment (+ 7 days if required for logistical and scheduling purposes), the patient will undergo the planned oncologic head and neck cancer surgery. The nature of complete resection of the primary head and neck

tumor, type of reconstruction, and levels of nodes to be dissected will be determined by the treating surgeon.

- Prior to surgery, standard of care dental evaluation is recommended, to allow for any necessary dental extractions to be planned in conjunction with surgery. Consultations with a Nutritionist and Speech and Language Pathologist are strongly recommended prior to surgery and as ongoing support post-operatively. Placement of a nasogastric (eg. Dobhoff) or gastrostomy feeding tube is at the discretion of the subject and the study physicians.
- Intraoperative tumor tissue for biomarkers (post-treatment tumor tissue collection)
 - Part of the tumor and/or lymph node specimen will be sent to the research laboratory for mandatory biomarker analyses.
 - If surgery is unexpectedly cancelled and the primary tumor or lymph node is accessible for in-office biopsy in the judgment of the surgeon-investigator, a tumor biopsy may be substituted for the intraoperative specimen.

Tissue collection procedures are described in Section 9.0.

6.3.2 Post-operative therapy

After surgery, subjects may receive adjuvant radiation or radiation plus chemotherapy in accordance with appropriate standards, as determined by the subject's treating physicians.

6.4 End-of-Treatment/Follow-up/Final Study Visit Procedures

6.4.1 4 week (+/- 2 weeks) follow-up visit

- History and physical examination
- Blood tests as clinically indicated (CBC, chemistries, liver function tests in accordance with investigator judgment)
- If pill count and medication diary did not occur previously, it will be done at the 4-week follow-up visit
- Adverse event follow up:
 - Events considered related to the study drug will be followed until return to baseline or stabilization.
 - During the post-treatment follow-up, only AEs considered related to the study drug need to be documented.
 - If a subject's surgery is cancelled but they received study drug, they will be assessed for adverse events at the 4 weeks (+/- 2 week) follow-up visit.

6.4.2 12 week (+/- 4 weeks) Final Study Visit

- History and physical examination
- Blood tests as clinically indicated (CBC, chemistries, liver function tests in accordance with investigator judgment)

6.4.3 Other visits

Additional non-protocol visits may occur during the 12-week post-operative period as deemed clinically necessary. Patients will be referred for adjuvant chemotherapy and radiation per standard of care, based upon pathologic findings.

Once the first 12 weeks of follow-up have been completed, study follow-up will be discontinued, and subjects will continue standard treatment and surveillance in accordance with national guidelines.

The standard post-operative visit which occurs 12 weeks post-op (+/- 4 weeks) will be considered the “final study visit.”

Table 6.1 Schedule of Study Procedures and Assessments/Study Calendar

Study Procedures	Baseline	Days 1 through 21	Days 22 through 28 (if surgery is delayed) ^k	Day of Surgery	4-Week Post-op Visit	Final Study Visit (12-week post-op) ^l
Informed consent	X					
History & physical examination ^a	X	To be performed between days 9 through 21			X	X
Vital signs, weight	X	To be performed between days 9 through 21			X	X
ECOG-PS	X	To be performed between days 9 through 21			X	X
Pregnancy test ^b	X					
EKG ^c	X					
Clinical blood tests ^d	X	To be performed between days 9 through 21			X	X
Cross-sectional imaging study ^e	X	To be performed between days 9 through 21				
MUGA or echocardiogram ^f	X					
p16 status	X					
Adverse Event Assessment		At each subject visit during treatment.			X	
Concomitant Medication Assessment	X	At each subject visit during treatment.				
Fasting plasma glucose	X	Every 7 days (+/- 3 days) while on BYL719	X			
Pill count/diary review		Diary review to be done at each visit. Pill count to be done when subject returns bottles and any extra pills.				
BYL719 ^g		Take medication Days 1 through 21	Continue BYL719 if surgery is delayed			
Surgery ^h		Surgery is to be performed day 11 or later.	Surgery may be performed day 22 through day 29.			
Research blood collection ⁱ	X	Complete within 5 days prior to surgery				

Biopsy for Research ^j	X			X		
----------------------------------	---	--	--	---	--	--

- a. History and physical examination within 8 weeks prior to study entry. This should include surgical assessment of the primary tumor, including fiberoptic nasopharyngoscopy or examination under anesthesia as indicated per standard of care, and as determined by the treating surgeon.
- b. Pre-menopausal women of child-bearing potential (WOCBP) must have a negative serum pregnancy test within 4 weeks of registration. A negative pregnancy test, serum or urine, must then be documented within 72 hours of Day 1 of BYL719 treatment.
- c. The standard of care EKG performed for pre-surgical evaluation should be used. EKGs performed within 12 weeks prior to study entry may be substituted, provided the patient has experienced no interval cardiac event.
- d. Clinical blood tests will be repeated once within 5 days prior to surgery, and at the 4 week and 12-week post-operative visits if clinically indicated according to the investigator. Blood tests include, CBC with differential, serum chemistries including fasting glucose, LFTs, coagulation studies, except **coagulation studies are not required at the 4 week or 12 week post-surgical visits**. Amylase, lipase, and HbA1c are done at baseline.
- e. Within 6 weeks of study entry (within 4 weeks preferred), and again within 5 days prior to planned surgery, patients will undergo cross-sectional radiological evaluation using diagnostic contrasted CT, PET/CT (with diagnostic contrasted CT), or MRI of regions with radiologically or clinically identifiable tumor.
- f. Cardiac imaging will be performed by Multiple Gated acquisition (MUGA) scan or Echocardiogram (ECHO) in order to assess the left ventricular ejection fraction (LVEF). MUGA or ECHO performed within 365 days prior to study entry may be substituted provided the patient has experienced no interval cardiac event.
- g. The first day of BYL719 treatment will be considered Day 1. BYL719 will be administered at 350 mg daily, for 10-21 days, and will be discontinued on the day prior to surgical resection. If surgery is delayed, the study drug may be continued until surgery, for a maximum of 28 days.
- h. Surgery will be scheduled during days 11-22 of BYL719 treatment. For logistical reasons, surgery may be delayed by up to 7 days (day 29). Postoperative complications, hospital days, and ICU days will be noted for each patient.
- i. Research blood samples will be obtained at baseline (prior to study drug administration, within 3 weeks of registration) and within the 5 days prior to scheduled surgery.
- j. Research biopsies will be obtained at baseline (prior to study drug administration, within 3 weeks of registration) and during planned surgery for resection of the tumor.
- k. If surgery is delayed, subjects will continue to take BYL719 until the day prior to surgery (maximum 28 doses). The pre-operative history and physical examination, pre-operative clinical blood tests, vitals, assessment of ECOG status and pre-operative imaging do not need to be repeated. Research blood may be drawn again.
- l. Patients will be seen for a standard 4 week post-operative visit (+/- 2 weeks), and again for a standard 12-week post-operative visit (+/- 4 weeks). Clinical blood tests will be obtained as deemed clinically necessary. Thereafter, patients will be followed off study per standard of care.

6.5 Usage of Concurrent/Concomitant Medications

In general, the use of any concomitant medication/therapies deemed necessary for the care of the patient is permitted, except as specifically prohibited.

Please refer to BYL719/alpelisib Investigator's Brochure.

All medications (excluding study treatment administered within 28 days prior to the administration of BYL) will be recorded in the Concomitant Medications log. Medications include not only physician prescribed medications, but also all over-the counter medications, herbal medications (prohibited, see Section 6.5.3 below) and food or vitamin supplements. The investigator should instruct the patient to notify the investigational site about any new medications he/she takes after the start of the study drug.

6.5.1 Dietary Restrictions

Patients will be instructed to avoid grapefruit products/juice, or Seville (sour) oranges/juice due to its potential for CYP3A4/5 interaction.

6.5.2 Permitted Concomitant Therapy Medications

In vitro metabolism studies performed to examine the reversible and metabolism-dependent inhibition of CYPP450 enzymes showed that BYL719, apart from the time-dependent inhibition of CYP3A4, is a weak, reversible inhibitor of CYP2C8, CYP2C9 and CPY2C19. Note that with the data available, it is not possible to confirm whether such interactions will occur in patients. Thus, caution should in principle be used in administering concomitantly drugs whose disposition is mainly dependent on these cytochrome P450 isoenzymes and whose therapeutic index is narrow.

As it has been shown that BYL719 is a substrate of BCRP transporter in vitro and since the impact of this interaction has not been clinically investigated yet, BCRP inhibitors should also be used with caution to avoid a transport-related drug-drug-interaction.

Patients receiving such medications must be monitored for potentiation of toxicity due to any individual concomitant medications and may require dose titration or reduction of the drug substrate.

Permitted medications to be used with caution during treatment with BYL719:

Antiemetics

Use of anti-emetics is allowed. Prophylactic anti-emetics should be started only once the patient experiences nausea or vomiting, at the discretion of the investigator. It is recommended that patients use drugs that do not cause QT prolongation. Please note that some anti-emetics have a known risk for TdP and are prohibited (refer to Appendix 3)

Oral anti-diabetic Agents

Patients who develop hyperglycemia during the study should be treated according to the ADA (American Diabetes Association) guidance. It is recommended to start treatment with metformin (or pioglitazone). Patients receiving oral antidiabetics which are predominantly metabolized by CYP2C9 and CYP2C8, including but not limited to, repaglinide, rosiglitazone, glipizide and

tolbutamide, must be carefully monitored for hypoglycemia as BYL719 was found to be a moderate reversible inhibitor of these enzymes (refer to Table 1).

Anticoagulation

Anticoagulants other than warfarin/coumarin derivates or antiaggregation agents may be administered under the discretion of the investigator. However, caution is advised when BYL719 is co-administered with anti-platelet pro-drugs such as clopidogrel, ticlopidine and prasugrel, which require metabolic activation by CYP3A4, CYP2C9 and CYP2C19. BYL719 has the potential to inhibit these enzymes and may therefore decrease the metabolic activation and clinical efficacy of these pro-drugs. Patients using anti-platelet pro-drugs should be carefully monitored (refer to Table 1).

Contraceptives

Hormonal contraceptives may be affected by cytochrome P450 interactions, and are therefore not considered effective for this study. For allowed contraception methods, refer to Exclusion Criteria. Highly effective contraception should be maintained throughout the study and through at least 1 weeks after the final dose of BYL719.

CYP450 substrates

In vitro studies demonstrate that BYL719 is a time dependent inhibitor of CYP3A4(K_i 5.6 μ M, Kinact 0.011 min-1). Reversible inhibition of CYP2C8 (K_i 32 μ M), CYP2C9 (K_i 22 μ M) and CYP2C19 (IC_{50} 75 μ M) was also observed. BYL719 may inhibit metabolic clearance of co-medication metabolized by CYP3A4, CYP2C8, CYP2C9 and CYP2C19, if sufficiently high BYL719 concentrations are achieved in vivo. Investigators, at their discretion, may administer concomitant medications known to be metabolized by or are substrates for CYP3A4/5, CYP2C8, CYP2C9 and CYP2C19. Patients receiving such medications and drugs which have a narrow therapeutic index must be carefully monitored for potential toxicity due to any individual concomitant medications. (Refer to Appendix 3).

Caution is advised when BYL719 is co-administered with opioid analgesics. Inhibition of opioid metabolism by CYP3A4 can lead to opioid toxicity, including fatal respiratory depression, or an enhanced risk for QTc prolongation. Patients receiving BYL719 and opioid analgesics should be carefully monitored. Synthetic opioids with clinically relevant interactions with CYP3A4 inhibitors include, but are not limited to, propoxyphene, fentanyl, alfentanyl and sufentanil. Use of alfentanyl, a sensitive CYP3A4 substrate with narrow therapeutic window, should be full avoided whenever possible. The use of methadone and levomethadyl is prohibited (Refer to Appendix 3).

Gastric protection agents

BYL719 is characterized by a pH-dependent solubility. Medicinal products that alter the pH of the upper gastro-intestinal tract may alter the solubility of BYL719 and hence its bioavailability. These agents include, but are not limited to, proton-pump inhibitors (PPI) (e.g., omeprazole), H₂-antagonists (e.g., ranitidine) and antacids. Due to long pharmacodynamic effect of PPIs, i.e. long-lasting reduction of gastric acid production over 36 hours, H₂-antagonists and antacids are recommended to be used over PPIs, whenever possible. Note that some proton pump inhibitors may possibly also inhibit BCRP (refer to Table 1). A drug-drug interaction study in human healthy volunteers confirmed that co-administration of alpelisib with the H2-antagonist ranitidine

after a meal lead to a decrease in exposure by only ~20%, considered to be not clinically relevant. Hence alpelisib can be co-administered with any ARAs.

BYL719 should preferably be dosed in a staggered manner, i.e., at least 1 hour before or 10 hours after dosing with a gastric protection agent.

BCRP inhibitors

BYL719 was identified as a substrate for the human BCRP. Co-administration of BYL719 with BCRP inhibitors may possibly increase systemic exposure and/or alter tissue uptake of oral BYL719. The treatment with BCRP inhibitors should be kept as short as possible or, if possible, fully avoided. See Appendix for Table of Permitted Medications.

6.5.3 Prohibited concomitant therapy

The following medications are prohibited during treatment in this study (see Appendix 3, this list is not comprehensive and is only meant to be used as a guide. Please contact the PI with any questions):

- Medications with a known risk for TdP
- Other investigational and antineoplastic therapies

In addition, the use of herbal preparations/medications and dietary supplements (except for vitamins) are prohibited throughout the study, as a potential drug-drug interaction is possible. Herbal medications include, but are not limited to: St. John's wort, Kava, ephedra (ma huang), gingko biloba, dehydroepiandrosterone, yohimbe, saw palmetto, black cohosh and ginseng. Patients should stop using all herbal medications and dietary supplements at least 7 days prior to first dose of study treatment.

As far as possible avoid co-administering QT prolonging drugs (or any other drug with the potential to increase the risk of drug-related QT prolongation e.g. via a potential DDI increasing the exposure of the study drug or the exposure of the QT prolonging drug). If during the course of the study, concomitant administration of drugs with a known potential to cause Torsades de Pointe is required and cannot be avoided, study drug must be interrupted until an assessment of the potential safety risk has been performed. A definitive list of drugs associated with QT prolongation and/or TdP is available online at www.crediblemeds.org. If, based on the investigator assessment and clinical need study treatment is resumed, close ECG monitoring is advised.

Metabolism studies in both human and animal liver preparations (microsomes, hepatocytes) showed a low metabolism of BYL719 by phase I and phase II metabolic enzymes.

Phenotyping studies in human liver microsomes confirmed that biotransformation mainly takes place via CYP3A4 (minor involvement of CYP2J2) with no major participation of UGTs. In vitro metabolism studies performed to examine the reversible and metabolism-dependent inhibition of cytochrome P450 enzymes showed that BYL719 is a time-dependent inhibitor of CYP3A4.

The following medications are therefore prohibited during treatment with BYL719:

Other anticancer therapy

If a patient, enrolled in the study, requires the concomitant use of any medication included in Appendix 3 entitled "List of Prohibited Medications during BYL719 Treatment" (i.e., drugs that are generally accepted by the Qtdrugs.org Advisory Board of the Arizona CERT to have a

known risk of causing TdP), BYL719 administration must be interrupted as long as the patient requires therapy with the QT prolonging agent. Note that Table 2 also prohibits drugs that are substrates for CYP3A and CYP2C with a possible or conditional risk for TdP. If the patient requires long term therapy with such a QT prolonging agent, leading to study treatment interruption of > 28 days, the patient must be permanently discontinued from BYL719.

Herbal medications

Herbal preparations/medications are not allowed throughout the study. These herbal medications include, but are not limited to St. John's wort, Kava, ephedra (ma huang), gingko biloba, dehydroepiandrosterone (DHEA), yohimbe, saw palmetto, and ginseng. Patients should stop using these herbal medications 7 days prior to first dose of study drug.

Warfarin and coumarin derivates

Therapeutic doses of warfarin sodium (Coumadin[®]) or any other coumarin-derivative anticoagulants are not permitted. Warfarin has a narrow therapeutic range and BYL719 is a possible inhibitor of CYP2C8 and 2C9, the major metabolizing enzyme of warfarin. Therapeutic anticoagulation may be accomplished using low-molecular weight heparin.

Radiation therapy must not be given with BYL719 to patients while the patient is treated. If radiation therapy is required for a patient then the patient must be discontinued.

7 Tumor Measurements

The primary objective of this study is to evaluate Δ Tumor size, which will be measured using established RECIST v1.1 metrics for target lesions, however treated as a continuous variable as previously described (23). Target lesions will be evaluated using the new international criteria proposed by the Response Evaluation Criteria in Solid Tumors (RECIST) Committee [JNCI 92(3):205-216, 2000]. Changes in only the largest diameter (unidimensional measurement) of the tumor lesions and the shortest diameter of metastatic lymph nodes are used in the RECIST v1.1 criteria.

NOTE: Because this is a pre-operative window study with only brief exposure to study drug, and RECIST responses are not anticipated, target lesions will be measured bi-dimensionally and recorded quantitatively. Quantitative change in the RECIST-defined baseline sum diameter (longest diameter of tumor + short axis diameter of up to three pathologic lymph nodes), expressed as a percent, will be the primary endpoint and will be correlated with biomarker modulation.

All tumor measurements pre- and post-treatment will be performed independently by a single neuroradiologist.

Evaluable for quantitative change in tumor size

Only those patients who have measurable disease present at baseline, have received at least 10 doses of BYL719, and have had their disease re-evaluated will be considered evaluable for change in tumor size.

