Warfarin and coumarin derivatives	Therapeutic doses of warfarin sodium (Coumadin®) or any other coumarin-derivative anticoagulants are prohibited in this study. Warfarin has a narrow therapeutic range and BYL719 is a possible inhibitor of CYP2C8 and 2C9, the major metabolizing enzyme of warfarin. Therapeutic anticoagulation may be accomplished using low-molecular weight heparin.
Drugs with a known risk for Torsades de Pointes / QT prolongation ⁵	Amiodarone, amitriptyline (2C19), arsenic trioxide, astemizole, cepridil, chloroquine, chlorpromazine, cisapride, citalopram, clarithromycin, clomipramine (2C19), disopyramide, dofetilide, domperidone, dronedarone (CYP3A4), droperidol, erythromycin, flecainide, halofantrine, haloperidol, ibutilide, levomethadyl, mesoridazine, methadone, moxifloxacin, pentamidine, pimozide, probucol, procainamide, quetiapine (3A4), quinidine, ritonavir (3A4), sotalol, sparfloxacin, tacrolimus (3A4), telithromycin (3A4), terfenadine, thioridazine, trazodone (3A4), vandetanib, vardenafil (3A4)

Category	Drug Name
¹ NTI = narrow therapeutic index drugs whose exposure-response indicates that increases in their exposure levels by the concomitant use of potent inhibitors may lead to serious safety concerns (e.g., Torsades de Pointes)	
² Herbal product	
³ P-gp inducer	
⁴ Sensitive substrates: Drugs whose plasma AUC values have been shown to increase 5-fold or higher when	
⁵ Please also refer to http://crediblemeds.org/ for a comprehensive list of agents that prolong the QT interval.	

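### Section 6.5.3 gives two different end-points for the BYL719 hold when a patient on study needs a drug with known torsades risk, and no text says which governs

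*Combined protocol and SAP*

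**What the plan says.** Section 6.5.3 prohibits medications with a known TdP risk during treatment. It then deals with the case where the prohibition cannot be kept, in two places.

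- **The QT paragraph** (after the paragraph on herbal preparations) applies if "concomitant administration of drugs with a known potential to cause Torsades de Pointe is required and cannot be avoided". Its instruction is that "study drug must be interrupted until an assessment of the potential safety risk has been performed". It continues: "If, based on the investigator assessment and clinical need study treatment is resumed, close ECG monitoring is advised".
- **The Appendix 3 paragraph** (under the sub-heading on other anticancer therapy) applies if an enrolled patient "requires the concomitant use of any medication included in Appendix 3", which it explains as drugs accepted to carry a known risk of causing TdP. Its instruction is that "BYL719 administration must be interrupted as long as the patient requires therapy with the QT prolonging agent". If that interruption exceeds 28 days, BYL719 is stopped permanently. It adds: "Note that Table 2 also prohibits drugs that are substrates for CYP3A and CYP2C with a possible or conditional risk for TdP".

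Appendix 3 has a row headed "Drugs with a known risk for Torsades de Pointes / QT prolongation" that lists the drugs by name. Section 6.5.3 describes the appendix as a guide that is not comprehensive. It also points to an external online list of QT and TdP drugs and invites questions to the principal investigator.

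**The concern.** The two paragraphs meet in the same patient: one on BYL719 who develops an unavoidable need for a drug in the known-TdP row. A site that follows the QT paragraph in good faith could restart BYL719 while the patient is still taking that drug, and so breach a mandatory arrhythmia precaution stated later in the same section. These patients are awaiting potentially curative surgery (10.3.2), and the rule is meant to work without case-by-case interpretation. The choice of rule also decides how many doses a patient loses, which bears on whether the patient reaches the 10 doses needed to be evaluable (sections 7 and 10.2.1).

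**Working it through.** The plan states no figure on this point, so the check is a comparison of texts, followed by two counts.

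**1. The rules side by side**

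| | QT paragraph | Appendix 3 paragraph |
|---|---|---|
| Trigger | Drug with known TdP potential, unavoidable | Any Appendix 3 drug, explained as known TdP risk |
| Hold ends | When the risk has been assessed | When the drug is no longer needed |
| Restart during co-administration | Contemplated, with ECG monitoring advised | Not allowed |

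**2. Test case.** A patient needs a drug from the known-TdP row for the rest of the window. Under the QT paragraph, BYL719 may restart after the assessment. Under the Appendix 3 paragraph it may not. The clause on interruptions above 28 days does not help, because treatment itself is capped at 28 days.

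**3. Could the QT paragraph mean a restart only after the drug has stopped?** This is the weaker reading. The trigger is that the drug cannot be avoided, the hold runs to the assessment and not to the end of the drug, and close ECG monitoring makes most sense if both drugs are being taken.

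**4. Is there a ranking elsewhere?** Footnote 1 of Appendix 2 places the caution list below other exclusions. The invitation to contact the principal investigator names a person to ask. Neither says when the hold ends.

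**5. Size of the overlap.** The known-TdP row of Appendix 3 names 41 drugs. Nine carry a CYP tag: amitriptyline, clomipramine, dronedarone, quetiapine, ritonavir, tacrolimus, telithromycin, trazodone and vardenafil. On the assumption that these are the possible- or conditional-risk drugs that the Appendix 3 paragraph mentions, the QT paragraph does not reach them, and 41 − 9 = 32 drugs fall under both rules. Without that assumption it is 41.

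Thirteen of the 41 also appear in other prohibited rows of Appendix 3:
- strong CYP3A inhibitors: clarithromycin, ritonavir, telithromycin;
- narrow-index CYP3A substrates: astemizole, cisapride, pimozide, quinidine, tacrolimus, terfenadine;
- sensitive CYP3A substrates: dronedarone, levomethadyl, quetiapine, vardenafil.

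That leaves 41 − 13 = 28 named only in the known-TdP row.

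**6. Dose margin.** The last dose is taken the day before surgery (6.2.2), so the dose days a patient can lose and still reach 10 are (surgery day − 1) − 10, assuming no other missed doses:
- surgery on day 11: 10 − 10 = 0;
- surgery on day 22: 21 − 10 = 11;
- surgery on day 29: 28 − 10 = 18.

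Section 6.2.4 prefers surgery on day 22 or later.

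**The case against.** The strongest defence is that the paragraphs are general and specific. The QT paragraph sets a minimum hold and then speaks conditionally of resumption; it never directs a restart. Because Appendix 3 is not comprehensive, that paragraph has work to do for unlisted drugs, while the Appendix 3 paragraph sets the stricter rule for listed ones. On this view a cross-reference is missing and nothing more. The reading is workable, but no sentence states it, and the QT paragraph's trigger has no exception for listed drugs.

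The second defence is that few patients could be affected, and this stands. Exclusion 7a in section 3.3.2 keeps out patients whose QT or TdP drugs cannot be stopped or switched, and QTcF above 480 msec at screening also excludes. Section 6.5 has patients told to notify the site of new medicines, and section 6.2.3 reviews medication on days 8, 15 and 22. What remains is a new, unavoidable need arising within a window of at most 28 days, in a trial of about 20 patients.

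Three stronger readings are tempting, and the documents do not support them.

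- *The two rules cannot both be obeyed.* They can: holding BYL719 for as long as the drug is needed satisfies both.
- *The QTcF stopping rule in section 5.6 would act only if the site did the ECGs that the QT paragraph advises.* Table 6.1 does schedule an EKG only at baseline, and footnote c shows that this may be the routine surgical one: "The standard of care EKG performed for pre-surgical evaluation should be used". But an ECG prompted by symptoms or any other clinical reason would also engage the rule.
- *The drug count measures harm.* It measures the length of a list. For the 13 drugs barred in other rows as well, a QT assessment alone would not clear co-administration.

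**Conclusion.** The point holds as an unresolved conflict over when a safety hold ends. For a required drug with known TdP risk, one paragraph of section 6.5.3 permits a restart of BYL719 that another paragraph of the same section forbids, and nothing says which governs. It concerns between 32 and 41 named drugs, depending on how the nine CYP-tagged ones are classed. The documents do not say how often such a drug would be needed, so no frequency or expected number of affected patients can be given. Existing safeguards narrow the exposure but do not settle the question for the patient in whom it arises. No endpoint definition, analysis or sample-size figure is affected; the only link to the analysis is through the 10-dose requirement. It deserves correction because it is a mandatory arrhythmia precaution and the correction is cheap.

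**What to change.** Amend the QT paragraph of section 6.5.3 to say that, for any drug with known TdP risk, whether listed in Appendix 3 or classed as known risk on the external list that the paragraph cites, BYL719 stays on hold for as long as the drug is required, as the Appendix 3 paragraph already states. Keep the route of assessment, restart and ECG monitoring only for QT-prolonging drugs that are below known TdP risk and not otherwise prohibited by Appendix 3.

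The line should follow risk class and not the list. Since Appendix 3 is not comprehensive, a list-based split would give an unlisted known-TdP drug the looser rule at the same risk.

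The cost is one or two sentences, with no added visit, ECG or calendar entry. The downside is that an occasional patient may fall below 10 doses and need replacing under section 10.2.2. This is likeliest when surgery is near day 11, where there is no margin, and less likely from day 22, where at least 11 dose days can be lost.
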